10.3 Safety Reporting

10.3.1 Reporting of Adverse Events

All AEs must be reported to the CRO through the eCRF and within the data entry timeline defined for this trial and stipulated in the clinical trial agreement.

10.3.2 Reporting of Adverse Events of Special Interest

All AESIs must be reported to the CRO through the eCRF and within two weeks following the event.

10.3.3 Reporting of Serious Adverse Events

All SAEs must be reported immediately and within a maximum of 24 hours to the CRO and thereafter the CRO will report to the Sponsor of the trial.

Serious adverse event primary information should be collected through the eCRF and the reporting is done via paper form, which can be submitted via email or fax to PRA Safety.

The contact information is:

- North/South America
- Fax: [REDACTED]
- Email: [REDACTED]

The Sponsor/CRO will re-evaluate the SAE and return the form to the site, requesting clarification or follow-up information if needed. After the initial SAE report, the Investigator is required, proactively, to provide further information regarding the subject's condition.

Serious AEs resulting in death will be reported to the IRB within 7 days.

The minimum data required for a report is:

- Subject identifier (ID)
- Trial ID
- Date of enrolment
- Date and time of start of SAE
- Description of SAE
- Severity of SAE
- Assessment of causality relationship to IMP
- Name and contact details of person reporting the event

10.3.4 Reporting of Suspected Unexpected Serious Adverse Events

A suspected unexpected serious adverse event (SUSAR) for an event that is life-threatening or fatal needs to be reported to the IRB (local event via local Investigator) and competent authorities (CAs) within 7 calendar days.

All other SUSARs need to be reported to the IRB (local event via local Investigator) and CAs within 15 calendar days.

As necessary, the Sponsor must inform the Investigator, the IRB, and competent authorities participating in the clinical trial of the occurrence of a SUSAR.

For SAEs, the active reporting period begins from the time that the subject provides informed consent through the end of the trial. Serious AEs occurring to a subject after the active reporting period has ended should be reported to the sponsor if the Investigator becomes aware of them; at minimum, all SAEs that the investigator believes have at least a reasonable possibility of being related to the IMP are to be reports to the Sponsor.

10.4 Pregnancy Reporting

Pregnancies occurring in this trial and within 90 days after dose are collected and reported. Unless described otherwise, pregnancies with or without serious outcomes are reportable within 24 hours of awareness to the CRO.

Although pregnancies themselves are not considered to be (S)AEs, the Investigator must report any pregnancies reported during the trial to the CRO within the timelines for SAE reporting. The trial subject will give consent on enrolment that the investigator will report any pregnancy occurring after consenting to 90 days after the dosing and that the subject will be asked to provide information about the pregnancy, delivery and the health of the infant until the age of 1 month. The Investigator must report information on pregnancies and follow-up within 14 calendar days of obtaining the information. Pregnancy complications must be recorded as (S)AEs, as appropriate. If the infant has a congenital anomaly/birth defect this must be reported and followed up as a SAE.

10.5 Medication Errors

Medication errors are reportable irrespective of the presence of an associated AE/SAE, including:

- Medication errors involving subject exposure to the IMP
- Potential medication errors or uses outside of what is foreseen in the protocol that do or do not involve the participating subject

Whether or not the medication error is accompanied by an AE, as determined by the Investigator, the medication error is captured on the medication error version of the AE page, and if applicable, any associated AE(s) are capture on the AE eCRF.

10.6 Severity Assessment

The Investigator will use the adjectives MILD, MODERATE, or SEVERE to describe the maximum intensity of the AE. For purposes of consistency, these are defined as follows:

- MILD: Does not interfere with subject's usual function
- MODERATE: Interferes to some extent with subject's usual function
- SEVERE: Interferes significantly with subject's usual function

Note the distinction between the severity and the seriousness of an AE. A severe event is not necessarily an SAE.

The NCI-CTCAE system [17] will be used to grade the severity of the SAEs, AEs and AESIs.

10.7 Causality Assessment

Both the Investigator and Sponsor will assess the causality of the event in relation to the IMP, based on the criteria listed in the ICH E2A guidelines [27]:

The Investigator must also systematically assess the causal relationship of AEs to IMP(s)/trial treatment (including any other non-IMPs, radiation therapy, etc.) using the definitions described below. Decisive factors for the assessment of causal relationship of an AE to the IMP include, but may not be limited to, temporal relationship between the AE and the IMP, known side effects of IMP, medical history, concomitant medication, course of the underlying disease, trial procedures.

Not related: Not reasonably related to the IMP. Adverse event could not medically (pharmacologically/clinically) be attributed to the trial IMP in this clinical trial protocol. A reasonable alternative explanation must be available. Adverse events reported as “unlikely” related and “unrelated” will be considered unrelated for reporting purposes.

Related: Reasonably related to the IMP. Adverse event could medically (pharmacologically/ clinically) be attributed to the IMP under trial in this clinical trial protocol. Table 10 can be used to differentiate between the AEs related to the IMP. Adverse events reported as definitely, probably and possibly related will be considered as “related” for reporting purposes.

Table 10: Assessment of Causality of Adverse Events

	Assessment of Causality				
	Definitely	Probably	Possibly	Unlikely	Not Related
Clearly due to extraneous causes	N	N	N	N	Y
Reasonable temporal association with drug administration	Y	Y	Y/N	N	N
May be produced by subject clinical state, etc.	N	N	Y	Y	Y
Known response pattern to IMP	Y/N	Y/N	N	N	N
Disappears or decreases on cessation or reduction in dose	Y	Y/N	N	N	N
Reappears on re-challenge (if possible)	Y	N	N	N	N

IMP=investigational medicinal product; Y=yes; N=no.

10.8 Adverse Event Outcome

An AE must be followed until recovery whether the trial has ended or not. The outcome must be classified according to the categories shown below:

- **Recovered/Resolved:** Resolution of an AE with no residual signs or symptoms
- **Recovered/Resolved with Sequelae:** Resolution of an AE with residual signs or symptoms
- **Recovering/Resolving:** Improvement of an AE
- **Not Recovered/Not Resolved (Continuing):** Either incomplete improvement or no improvement of an AE such that it remains ongoing
- **Fatal:** The outcome of an AE is death. “Fatal” must be used when death is at least possibly related to the AE
- **Unknown:** The outcome of an AE is not known (e.g., a subject lost to follow-up)

10.9 Treatment Given

The Investigator must ensure adequate medical care is provided to subjects for any AEs. In addition, the Investigator must describe whether any treatment was given for the AE. This information must be documented on subject source.

10.10 Liver Safety: Suggested actions and Follow-up Assessments for Potential Cases of Drug-Induced Liver Injury

Humans exposed to a drug who show no sign of liver injury (as determined by elevations in transaminases) are termed “tolerators,” while those who show transient liver injury, but adapt are termed “adaptors.” In some subjects, transaminase elevations are a harbinger of a more serious potential outcome. These subjects fail to adapt and therefore are “susceptible” to progressive and serious liver injury, commonly referred to as drug-induced liver injury (DILI). Subjects who experience

a transaminase elevation above $3 \times \text{ULN}$ should be monitored within 48 hours and alternate causes of hepatitis should be investigated to determine if they are an “adaptor” or are “susceptible.”

In the majority of DILI cases, elevations in AST and/or ALT precede total bilirubin (TBili) elevations ($>2 \times \text{ULN}$) by several days or weeks. The increase in TBili typically occurs while AST/ALT is/are still elevated above $3 \times \text{ULN}$ (i.e., AST/ALT and TBili values will be elevated within the same laboratory sample). In rare instances, by the time TBili elevations are detected, AST/ALT values might have decreased. This occurrence is still regarded as a potential DILI. Therefore, abnormal elevations in either AST OR ALT in addition to TBili that meet the criteria outlined below are considered potential DILI (assessed per Hy’s law criteria; [19]) cases and should always be considered important medical events, even before all other possible causes of liver injury have been excluded.

The threshold of laboratory abnormalities for a potential DILI case depends on the subject’s individual baseline values and underlying conditions. Subjects who present with the following laboratory abnormalities should be evaluated further as potential DILI (Hy’s law) cases to definitively determine the etiology of the abnormal laboratory values:

Discontinuation of treatment should be considered if:

- ALT or AST $>8 \times \text{ULN}$
- ALT or AST $>5 \times \text{ULN}$ for more than 2 weeks
- ALT or AST $>3 \times \text{ULN}$ and (TBL $>2 \times \text{ULN}$ or INR >1.5)
- ALT or AST $>3 \times \text{ULN}$ with the appearance of fatigue, nausea, vomiting, right upper quadrant pain or tenderness, fever, rash, and/or eosinophilia ($>5\%$)

Rises in AST/ALT and TBili separated by more than a few weeks should be assessed individually based on clinical judgment; any case where uncertainty remains as to whether it represents a potential Hy’s law case should be reviewed with the sponsor.

The subject should return to the Investigator site and be evaluated as soon as possible, preferably within 48 hours from awareness of the abnormal results. This evaluation should include laboratory tests, detailed history, and physical assessment.

In addition to repeating measurements of AST and ALT and TBili for suspected cases of Hy’s law, additional laboratory tests should include albumin, creatine kinase, direct and indirect bilirubin, gamma-glutamyl transferase, prothrombin time/international normalized ratio, total bile acids, and alkaline phosphatase. Consideration should also be given to drawing a separate tube of clotted blood and an anticoagulated tube of blood for further testing, as needed, for further contemporaneous analyses at the time of the recognized initial abnormalities to determine etiology. A detailed history, including relevant information, such as review of ethanol, acetaminophen (either by itself or as a co-formulated product in prescription or over-the-counter medications), recreational drug, supplement (herbal) use and consumption, family history, sexual history, travel history, history of contact with a jaundiced person, surgery, blood transfusion, history of liver or allergic disease, and potential occupational exposure to chemicals, should be collected. Further testing for acute hepatitis A, B, C, D, and E infection and liver imaging (e.g., biliary tract) and collection of serum sample for acetaminophen drug and/or protein adduct levels may be warranted.

All cases demonstrated on repeat testing as meeting the laboratory criteria of AST/ALT and TBili elevation defined above should be considered potential DILI (Hy's law) cases if no other reason for the liver function test (LFT) abnormalities has yet been found. **Such** potential DILI (Hy's law) cases are to be reported as SAEs, irrespective of availability of all the results of the investigations performed to determine etiology of the LFT abnormalities.

3.0 Introduction

This Statistical Analysis Plan (SAP) describes the statistical methods that will be used during the analysis and reporting of data collected under VectivBio AG Protocol TA799-014.

This SAP should be read in conjunction with the study protocol and electronic case report form (eCRF). This version of the plan has been developed using the protocol dated 11-Sep-2020 (including all amendments up to this protocol date) and the final eCRF(s) dated 21-Sep-2020.

An approved and signed SAP is a requirement for database lock. An approved SAP is also required for unblinding of the study treatments.

This SAP only covers the results that will be processed by the PRA Early Development Services (EDS) Biostatistics Department.

PRA EDS will perform the pharmacokinetic (PK), safety and tolerability evaluation.

This SAP supersedes the statistical considerations identified in the protocol; where considerations are substantially different, they will be so identified. Any post-hoc or unplanned analyses, or significant changes from the planned analysis in this SAP performed to provide results for inclusion in the clinical study report (CSR) but not included in this SAP, will be clearly identified in the CSR. Changes to planned analyses do not require an updated SAP but should be included in the CSR if significant.

4.0 Changes from Previous Version of Approved SAP

This is the first version of the SAP.

5.0 Study Objectives

5.1 Primary

Part 1 of clinical trial: To assess the PK of apraglutide in subjects with severe renal impairment compared to matched control subjects with normal renal function following single subcutaneous (SC) dose administration.

Part 2 of clinical trial (if applicable): To assess the PK of apraglutide in subjects with moderate and mild renal impairment compared to matched control subjects following single SC dose administration.

5.1.1 Primary Endpoint

Plasma apraglutide PK parameters: C_{max} and AUC_{inf}, AUC_{last}, AUC_{0-7days}, T_{max}, λ_z, t_{1/2}, CL/F, V_z/F. C_{max} and AUC_{inf} or AUC_{last} as primary PK parameters. All others as secondary PK parameters.

5.2 Secondary

To assess the safety and tolerability of apraglutide administered to subjects with varying degrees of impaired renal function.

5.2.1 Secondary Endpoint

Adverse event (AE) (type, frequency and intensity), AE of Special Interest (AESIs), vital signs (systolic and diastolic blood pressure (BP), heart rate), recorded triplicate electrocardiogram (ECG) (intervals, rhythm, and morphology), clinical chemistry, hematology, and urinalysis.

6.0 Study Design

This is a Phase 1, non-randomized, open-label, single-dose trial to evaluate the effect of varying degrees of impaired renal function on the PK, safety, and tolerability of apraglutide administered to trial subjects by SC injection in a clinical research unit (CRU). A staged approach, as outlined below, will be followed in the trial. Subjects will be selected and categorized into normal renal function or renal impairment groups based

on their estimated glomerular filtration rate (eGFR) which will be calculated using the Chronic Kidney Disease Epidemiology (CKD-EPI) Creatinine Equation ([Table 1](#)).

Table 1: CKD-EPI Equation

Part 1

Cohort ^a	eGFR (mL/min/1.73 m ²) ^b	N
1 (Severe Renal Impairment)	<30 not on hemodialysis	8
2 (Normal Healthy Match)	≥90	8

Part 2

Cohort ^a	eGFR (mL/min/1.73 m ²) ^b	N
3 (Moderate Renal Impairment)	≥30 to <60	8
4 (Mild Renal Impairment)	≥60 and <90	8

^a. Stages of Renal Impairment are based on the Kidney Disease Outcomes Quality Initiative (KDOQI) Clinical Practice Guidelines for Chronic Kidney Disease (CKD).

^b. Estimated glomerular filtration rate (eGFR) based on Chronic Kidney Disease Epidemiology (CKD-EPI). The baseline eGFR will be obtained by taking the mean of the eGFR obtained from screening and from historical values within a 3-month period from screening. If no historical measurement is available, a second baseline eGFR sample will be taken during the screening period (≥72 hours apart, but no more than 14 days apart) and the mean of the two values will be used for the group assignment; the second baseline eGFR sample may be obtained at the time of check-in. Subjects will be assigned to one of the 4 renal function groups based on eGFR values at screening. Estimated GFR will be calculated using the CKD-EPI Creatinine Equation:

$$eGFR = 141 \times \min(SCr/\kappa, 1)^\alpha \times \max(SCr/\kappa, 1)^{-1.209} \times 0.993^{Age} \times 1.018 \text{ [if female]} \times 1.159 \text{ [if black]}$$

Notes: eGFR is expressed as mL/min/1.73 m² of body surface area, SCr (serum creatinine) is expressed in mg/dL

κ = 0.7 (females) or 0.9 (males)

α = -0.329 (females) or -0.411 (males)

min = indicates the minimum of SCr/ κ or 1

max = indicates the maximum of SCr/ κ or 1

age is in years

Reasonable efforts will be made to enroll at least two subjects with eGFR values of <20 mL/min/1.73 m²

Part 1 of clinical trial: A total of approximately 16 subjects will be enrolled in Part 1: approximately eight subjects with severe renal impairment (Cohort 1) and approximately eight subjects with normal renal function (Cohort 2) to ensure at least six evaluable subjects in each group. Subjects from the severe renal impairment group will be recruited first. The demographics will be pooled across enrolled subjects to determine an average value for age and weight in the severe impairment group. Subsequently, the healthy subjects will be recruited later such that each subject's age is within ±10 years and weight is within ±15 kg of the mean of the severe renal impairment group. Attempts will be made to maintain a similar male/female ratio composition between groups. Care will be taken when recruiting the healthy subjects such that the entire group is not of substantially different age or of substantially different body weight than the severely renally impaired subjects.

Criteria to proceed to Part 2: After evaluation from Part 1, Part 2 will be conducted if the point estimate of apraglutide area under the concentration-time curve from time 0 to infinity (AUC_{inf}, or to the time of the last quantifiable concentration (AUC_{last}), if AUC_{inf} cannot be calculated) geometric mean ratio (GMR) for the severe renal impairment group compared to the control group (normal renal function group) is ≥2.

If criterion is not met, the trial will stop after Part 1. If there are subjects who withdraw or discontinue treatment from the normal or severe renal impairment groups and who are considered to be non-evaluable with respect to the primary PK objective, replacement subjects can be enrolled at the discretion of the sponsor.

Part 2 of clinical trial: If the decision criterion to proceed to Part 2 is met, approximately eight subjects each with moderate (Cohort 3) and mild (Cohort 4) renal impairment will be enrolled to ensure at least six

[figure not shown]
evaluable subjects in each group. As in Part 1, renal impairment classification will be based on eGFR. Healthy subjects will not be enrolled in Part 2. Healthy subjects from Part 1 will be used as the control group of the moderate and mild renal impairment subjects.

When recruiting the Part 2 subjects, attempts to match the entire group to the subjects in Part 1 with respect to age, sex, and body weight will be made. Other demographics such as race and ethnicity may be considered for matching the Part 1 and Part 2 populations when possible.

As in Part 1, if there are subjects who withdraw or discontinue treatment from the moderate or mild impairment group and who are considered to be non-evaluable with respect to the primary PK objective, additional subjects can be enrolled at the discretion of the Sponsor.

Screening will occur within a 28-day window prior to dosing. Subjects will be admitted on Day -1; on Day 1 a single SC injection of 5 mg apraglutide will be administered followed by blood PK sampling for 240 hours (Day 11). All subjects who received the apraglutide (including subjects who terminate the trial early) will return to the CRU approximately 14±2 days after dosing for the end of trial (EOT) visit where follow-up assessments will be performed according to the Schedule of Assessments and to determine if any adverse events (AEs) have occurred since the last trial visit.

Figure 1 Trial Schematic

CRU=clinical research unit; PK=pharmacokinetics; SC=subcutaneous

6.1 Sample Size Considerations

No formal power calculation was performed. The number of subjects per group is based on the review of the literature and of the European Medicine Agency (EMA) and the USA Food and Drug Administration (FDA) guidelines. While the EMA suggests 6–8 subjects per group, the FDA draft guidance does not provide an exact number of renal impaired patients needed for such a clinical trial.

The sample size of eight subjects per group is also based on the feasibility to recruit subjects with severe renal impairment.

6.2 Randomization

This is an open-label, single-sequence study; no randomization or blinding will be conducted.

7.0 Overview of Planned Analysis

7.1 Changes from Protocol

There are no changes from the protocol.

7.2 Interim Analysis and Key Results

There will be no interim analyses or summaries of data provided prior to the delivery of the full set of post-lock tables, figures and listings (TFLs).

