
Trial design
 
A Phase 1, non-randomized, open-label, single-dose trial to evaluate the effect of varying degrees of impaired renal function on the PK, safety, and tolerability of apraglutide administered to trial subjects by SC injection in a clinical research unit (CRU). A staged approach, as outlined below, will be followed in the trial. Subjects will be selected and categorized into normal renal function or renal impairment groups based on their estimated glomerular filtration rate (eGFR) which will be calculated using the Chronic Kidney Disease Epidemiology (CKD-EPI) Creatinine Equation [16]:
 $eGFR = 141 \times \min(SCr/\kappa, 1)^\alpha \times \max(SCr/\kappa, 1)^{-1.209} \times 0.993^{Age} \times 1.018 [\text{if female}] \times 1.159 [\text{if black}]$ 
Notes eGFR is expressed as mL/min/1.73 m² of body surface area, SCr (serum creatinine) is expressed as mg/dL, $\kappa = 0.7$ (females) or 0.9 (males), $\alpha = -0.329$ (females) or -0.411 (males), min = indicates the minimum of SCr/κ or 1, max = indicates the maximum of SCr/κ or 1, age is in years.
 
Part 1 of clinical trial: A total of approximately 16 subjects will be enrolled in Part 1: approximately eight subjects with severe renal impairment (Cohort 1) and approximately eight subjects with normal renal function (Cohort 2) to ensure at least six evaluable subjects in each group. Subjects from the severe
	

renal impairment group will be recruited first. The demographics will be pooled across enrolled subjects to determine an average value for age and weight in the severe impairment group. Subsequently, the healthy subjects will be recruited later such that each subject's age is within ± 10 years and weight is within ± 15 kg of the mean of the severe renal impairment group. Care will be taken when recruiting the healthy subjects such that the entire group is not of substantially different age or of substantially different body weight than the severely renally impaired subjects.

Criteria to proceed to Part 2: Part 2 will be conducted if after evaluation from Part 1, the point estimate of apraglutide area under the concentration-time curve from time 0 to infinity (AUC_{inf}) or to the time of the last quantifiable concentration AUC_{last} geometric mean ratio (GMR) for the severe renal impairment group compared to the control group is ≥ 2 (Section 3.1.1).

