1.2 Rationale

This trial is a Phase 1, non-randomized, open-label, single dose, parallel-group trial of apraglutide in subjects with severe renal impairment and subjects with normal renal function (Part 1) and in subjects with mild and moderate renal impairment (Part 2) matched for age and body weight. Details on the age and body weight matching criteria are specified in Section 4 of the protocol.

Since the metabolic pathway of apraglutide is expected to be degradation into small peptides and amino acids via catabolic pathways, similar to the catabolism for endogenous GLP-2, and in keeping with previous nonclinical and clinical pharmacokinetic trials that demonstrated no intact parent compound being recovered from the urine, it is not expected that renal impairment will have an impact on the PK of apraglutide. Therefore, a reduced, adaptive trial design will be pursued. In this trial design, only subjects with severe renal impairment and normal renal function will be studied first. In this manner, the effect of renal impairment on apraglutide PK will be initially evaluated in the renal impaired population most likely to be of impact. The impact of renal impairment expression of cytochrome P450 (CYP) enzymes, if any, is expected to be minimal and hence can also be evaluated in the severely renally impaired population to estimate degree of impact. If the trial results confirm that severe renal impairment does not alter PK to an extent that warrants dose adjustment, no further trial is warranted. If the results do not support such a conclusion, Part 2 will be conducted in subjects with moderate and mild renal impairment, based on the decision criteria outlined in Section 3.

Single-dose of SC apraglutide PK appears to be linear in the dose ranges between 2.8 mg to 56.9 mg relative to C_{max} and AUC_{inf} . No direct enzyme inhibition/induction or time-dependent enzyme inhibition is expected. The absolute bioavailability was 24.6% and the terminal half-life ($t_{1/2}$) was approximately 30 hours. Considering a linear PK at the therapeutic dose range being tested in Phase 2 trials (5–10 mg) in which single-dose PK behavior can predict multiple dose PK, a single-dose trial will be conducted to evaluate apraglutide PK under conditions of renal impairment.

The trial will use a single dose of 5 mg apraglutide administered via SC injection.

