3.1.1 Part 1 of Clinical Trial

A total of approximately 16 subjects will be enrolled in Part 1; approximately eight subjects with severe renal impairment (Cohort 1) and approximately eight with normal renal function (Cohort 2) to ensure at least six evaluable subjects in each group. Subjects from the severe renal impairment group will be recruited first. The demographics will be pooled across enrolled subjects to determine an average value for age and weight in the severe impairment group. Subsequently, the healthy subjects will be recruited later such that each subject's age is within ± 10 years and weight is within ± 15 kg of the mean of the severe renal impairment group. Care will be taken when recruiting the healthy subjects such that the entire group is not of substantially different age or of substantially different body weight than the severely renally impaired subjects.

Criteria to proceed to Part 2: After evaluation from Part 1, Part 2 will be conducted if the point estimate of apraglutide area under the concentration-time curve from time 0 to infinity (AUC_{inf} or AUC_{last} [if AUC_{inf} cannot be calculated]) geometric mean ratio (GMR) for the severe renal impairment group (compared to the normal group as control) is ≥ 2 . This metric is supported by recommendations from Huang *et al* [14]. Furthermore, apraglutide was well tolerated up to 56.9 mg SC QW and very well tolerated at 28.4 mg SC QW, further demonstrating the large therapeutic margin of apraglutide. If this criterion is not met, the trial will stop after Part 1.

If there are subjects who withdraw or discontinue treatment from the normal or severe renal impairment groups and who are considered to be non-evaluable with respect to the primary PK objective, additional subjects can be enrolled at the discretion of the sponsor.

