8.3 Statistical Analysis

The Statistical Analysis Plan (SAP) will be developed and finalized prior to database lock. The SAP will describe the subject populations to be included in the analysis. Unless otherwise noted in SAP, missing values will not be imputed. An explanation will be given for any missing, unused, and spurious data affecting analysis in the relevant sections of the Clinical Trial Report (CTR). This section is a summary of the planned statistical analysis of the primary and secondary endpoints.

Part 1

Analysis of variance (ANOVA) will be used to compare the natural log transformed AUC_{inf} or AUC_{last} (if AUC_{inf} cannot be calculated) and C_{max} for apraglutide between normal renal function group (Reference) and the severe impaired renal group (Test). Estimates of the mean differences (Test-Reference) and corresponding 90% CIs will be obtained from the model. The mean differences and 90% CIs for the differences will be exponentiated to provide estimates of the ratio of the adjusted geometric means (Test/Reference) and 90% CIs for the ratios.

Part 2 may be conducted if apraglutide AUC_{inf} (or AUC_{last} when AUC_{inf} cannot be calculated) GMR for severe renal impairment group compared to normal group is ≥ 2.0 . This metric is supported by recommendations from Huang *et al* [14]. Furthermore, apraglutide was well tolerated up to 56.9 mg SC QW and very well tolerated at 28.4 mg SC QW further demonstrating the large therapeutic margin of apraglutide.

Part 2

Analysis of variance will be used to compare the natural log transformed AUC_{inf} or AUC_{last} and C_{max} for apraglutide between normal renal function group from Part 1 (Reference) and each of the moderate and mild impaired renal groups (Test). Estimates of the mean differences (Test-Reference) and corresponding 90% CIs will be obtained from the model. The mean differences and 90% CIs for the differences will be exponentiated to provide estimates of the GMR (Test/Reference) and 90% CIs for the ratios.

Box and whisker plots for individual subject parameters (AUC_{inf} or AUC_{last} and C_{max}) will be constructed by renal function group and overlaid with geometric means.

For summary statistics and median/mean plots by sampling time, the nominal PK sampling time will be used. For individual subject plots by time, the actual PK sampling time will be used.

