7.3 Final Analysis

Draft TFLs will be provided after database lock. After Sponsor comments have been incorporated, the TFLs will be finalized and incorporated in the first draft CSR.

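### Does the SAP's ban on interim summaries block the Part 1 estimate that decides whether Part 2 runs?

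*SAP*

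**What the plan says.** **The gate.** Protocol 3.1.1 reads "After evaluation from Part 1, Part 2 will be conducted if the point estimate of apraglutide area under" the concentration-time curve gives a severe/normal GMR of 2 or more. The protocol synopsis ("Part 2 will be conducted if after evaluation from Part 1, the point estimate of apraglutide") and SAP 6.0 ("Part 2 will be conducted if the point estimate of apraglutide area under the concentration-time curve from time 0 to infinity") set the same rule. If it is not met, the trial ends after Part 1.

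**Timing of results.** SAP 7.2 states "There will be no interim analyses or summaries of data provided prior to the delivery of the full set" of post-lock tables, figures and listings. SAP 7.3 states "Draft TFLs will be provided after database lock". Neither section mentions a lock or delivery for Part 1.

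**Models.** SAP 16.2.2.1 gives a Part 1 ANOVA for severe against normal. A separate Part 2 ANOVA compares moderate and mild with the Part 1 normal group. If Part 2 runs, the AUC GMRs and 90% CIs for all three impaired groups are plotted together. Appendix 3 lists one ANOVA table, 14.2.3.1.

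**Wording of the gate.** Protocol 1.2 says "If the results do not support such a conclusion, Part 2 will be conducted in subjects with moderate and mild renal impairment", leaving the criterion to Section 3. Protocol 8.3 says "Part 2 may be conducted if apraglutide" shows a GMR of at least 2.0.

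**The concern.** Three things look wrong at first.

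1. The trial's only adaptive decision needs a Part 1 result before Part 2 enrols. A ban on any summary before the full post-lock set, next to one unqualified lock, appears to forbid that result. Taken literally, the decision would either break the SAP or rest on data whose cut-off was never defined.
2. If the gate is met, the severe/normal comparison is used twice: for the decision and in the final three-group plot. The Part 2 contrasts carry four coefficients, so the severe group is in that model. The reported interval could then come from a different fit than the one seen at the decision.
3. *May* in protocol 8.3 would give the sponsor a choice after seeing open-label data, whereas *will* makes the gate binding.

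**Working it through.** The plan states no figure to reproduce: no power calculation was done, and SAP 9.4.3 rules out formal hypothesis testing. The check is a reading of the text, plus one calculation for the refit question.

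**Step 1: can SAP 7.2 be followed?**
- SAP 6.0 says "A staged approach, as outlined below, will be followed in the trial" and puts the evaluation of Part 1 before Part 2.
- The protocol synopsis dates the last Part 1 visit to March 2021 and the start of Part 2 to May 2021, which leaves a gap for the analysis.
- The trial may end at Part 1. In that case the Part 1 lock is the only lock and the Part 1 outputs are the full set.
- The Part 1 ANOVA is the planned primary analysis of Part 1. Delivering it after Part 1 is complete and locked is not an unplanned look at accumulating data.

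The other reading, a single lock after Part 2, cannot be carried out, because Part 2 could never be triggered. Only one workable reading remains.

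**Step 2: which severe/normal result is reported?**
The Part 2 text and code contain contrasts for moderate and mild only. The only severe/normal estimate that the SAP defines is the Part 1 one, so the three-group plot takes it from there. A refit would need a contrast that is not in the SAP.

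**Step 3: what would a refit change?**
Inputs:
- n = 8 per group planned, with at least 6 evaluable (SAP 6.0);
- 90% CIs (SAP 16.2.2.1);
- CV 35% on clearance (protocol 1.3.2.1), assumed to apply to AUC in every group;
- GMR = 2.0, the gate value.

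Formulas:
- log-scale SD = √ln(1 + CV²) = √ln(1.1225) = 0.340;
- SE = SD × √(2/n);
- CI = GMR ÷ and × exp(t × SE), with t the 0.95 quantile.

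For n = 8, SE = 0.340 × √(2/8) = 0.170.

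| n per group | Fit | Residual df | t | exp(t × SE) | 90% CI at GMR 2.0 |
|---|---|---|---|---|---|
| 8 | two groups | 2(8−1) = 14 | 1.761 | 1.349 | 1.48–2.70 |
| 8 | four groups | 4(8−1) = 28 | 1.701 | 1.335 | 1.50–2.67 |
| 6 | two groups | 2(6−1) = 10 | 1.812 | 1.427 | 1.40–2.85 |
| 6 | four groups | 4(6−1) = 20 | 1.725 | 1.403 | 1.43–2.81 |

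With other assumed CVs and n = 8, the interval moves from 1.61–2.48 to 1.62–2.47 at 25%, and from 1.32–3.03 to 1.34–2.99 at 50%.

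The GMR is the exponentiated difference of two group means on the log scale, so adding other groups to a one-way ANOVA does not alter it. A simulated data set gave 1.9125 from both fits. The gate uses only this point estimate.

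**Step 4: *will* against *may*.**
*Will* appears in the protocol synopsis, protocol 1.2, protocol 3.1.1 and SAP 6.0: four places, of which protocol 1.2 gives no threshold of its own. *May* appears once, in protocol 8.3, which calls itself a summary of the planned analysis. The threshold is 2 wherever it is stated. SAP 3.0 gives the SAP precedence on statistical considerations, and the SAP says *will*.

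**The case for a change.** The best case for a change is that an SAP should state the data cut behind its only adaptive decision and should not leave it to be inferred from the design. It should also name the fit that supplies each reported interval, since the table above assumes the same variability in every group. Observed residual variances will differ. In the simulated data set, with a true log SD of 0.34 in all four groups, the interval went from 1.58–2.31 (two groups) to 1.46–2.50 (four groups), which is more than the change in degrees of freedom alone would give. Finally, SAP precedence does not cure a protocol that disagrees with itself.

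The text could indeed be tighter, and the word *lock* could be qualified by part. The rest carries little weight. The larger shift in the interval arises only if someone adds a contrast that the SAP does not contain, and even then both fits are valid ANOVAs with the same GMR. The *may* in protocol 8.3 does not create the sponsor's freedom to stop: protocol 5.3 already allows early termination at the sponsor's discretion. Using it would leave the moderate and mild groups unstudied but would not bias the Part 1 estimate. The Data Management Plan (SAP 8.1) and the table shells (SAP 9.5) may also settle the locks and the table rows. They are not available here, and the conclusion does not depend on them.

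**Conclusion.** The concern is accurate on the text but calls for no change. The missing Part 1 lock is a gap with only one workable filling, and any analyst following the staged design would fill it that way. The source of the severe/normal result is settled by the only contrast the SAP provides. The *may* in protocol 8.3 is a clerical mismatch with an identical threshold.

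On the same data, the GMR and the gate decision are the same on every reading. The only quantity that could differ is the severe/normal 90% CI, and only if Part 2 runs and an unplanned refit is reported. Its expected size is 1.48–2.70 against 1.50–2.67 at n = 8 and GMR 2.0, and no rule in the plan depends on it. Those figures assume that the 35% CV for clearance carries over to AUC and is equal across groups. The unchanged GMR does not depend on that assumption; it requires only that the severe and normal data stay the same between the decision and the final report.
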